5.3 Baseline Procedures

During this period, we will get baseline assessments of parameters of interest.

5.3.1 Baseline Visit 1

- Return 24-hour urine collection to measure phosphorus, creatinine, calcium, and urea in the urine
- Random urine sample to measure phosphorus, creatinine, and calcium in the urine
- 8-hour CRU stay for 8-hour timed urine collection to measure phosphorus, creatinine, calcium and urea in the urine
- Plasma chemistries (creatinine, phosphate, calcium)
- Blood draw for correlative studies (PTH, FGF23, P1NP, CTX)
- Blood draw for optional study elements (PTH, FGF23, P1NP, CTX)
- Distribute supplies for 24-hr urine collection

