5.4 Procedures During Treatment

During this period, participants will be randomized to the intervention arms (Baseline 2/ Follow up visit 0), have two 8-hour visits (Baseline visits 1 and Follow up visit 5) and will make visits to the CTMH every 3 days (Follow up visits 1 – 4).

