5.4.1 Baseline 2/Follow-up Visit 0 (F0)

- Return 24-hour urine collection to measure phosphorus, creatinine, calcium, and urea in the urine
- Random urine sample to measure phosphorus, creatinine, and calcium in the urine
- Plasma chemistries (NA, K, Cl, HCO3, BUN, Cr, glucose, phosphate, calcium)
- Blood draw for correlative studies (PTH, FGF23)
- Randomization to interventions
- Distribute study drug/placebo
- Distribute supplies for next 24-hr urine collection

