10.2 Sample Size and Accrual

Assumptions based on prior studies:

- Data on effects of nicotinamide on blood or urine phosphate in healthy volunteers are not available.
- Similarly, data on the combined use of the nicotinamide and lanthanum carbonate are lacking.
- Therefore, we relied on published data of the effects on lanthanum carbonate on 24-hour urine phosphate. In previous short-term studies of healthy volunteers, lanthanum carbonate at the dose that we will use in our study decreased 24-hour urine phosphate by 236 to 468 mg/day.²⁹ The within group standard deviation of change in 24-hour urine phosphate ranged from 168 to 294 mg/day.²⁹

Derivation of the sample size for this study:

Using the PS Power and Sample Size calculator (independent t test), we estimated that a sample size of 20 participants per group will yield 80% power to detect a difference of 273 mg/dl in urine phosphate, at $\alpha=0.05$, assuming a within group SD of the change in 24-hour urine phosphate of 300 mg/day. Assuming a conservative within group SD of the change in plasma phosphate of 0.55 mg/dl, the sample size of 20 volunteers per group will allow us to detect a difference as small as 0.50 mg/dl in plasma phosphate.

Importantly, we based our power calculations on t-tests that compare pre to post intervention changes across two groups. Because the repeated measures analyses we will employ using linear mixed models will reduce within-subject variability, we expect to have more power than is tabulated above and view the presented power calculations as conservative estimates. Additionally, power for main effects analyses (effects of lanthanum carbonate alone and nicotinamide alone; 40 participants per groups; margin comparison) will be greater than the presented power for comparisons of dual treatment to placebo (20 participants per group; individual cell comparison).

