10.3 Data Analyses Plans

- We will study changes over time in absolute levels of the primary and secondary end-points.
- We will use mixed-model, repeated-measures analyses to assess the changes.
- Model terms will include:
 - fixed-effects treatment terms (treatment group);
 - the interaction between each treatment and time (nicotinamide x time and lanthanum carbonate x time);
 - the interaction between treatments (nicotinamide x lanthanum carbonate);
 - the interaction between treatments and time (nicotinamide x lanthanum carbonate x time);
 - random-effects terms, connoting individual participants.
- If the interaction term between treatments and time (nicotinamide x lanthanum carbonate x time) is significant, we will compare the response in the dual intervention group to the placebo group.
- If the interaction term between treatments and time (nicotinamide x lanthanum carbonate x time) is not significant, we will examine the main effects of each intervention.
- We will use natural log transformation for end points with skewed distribution.
- If there are significant differences ($p<0.05$) in age, gender and baseline eGFR across randomized treatment groups, we will adjust for these covariates.
- Standard descriptive analyses will be used for safety evaluations.

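### Section 10.3 does not say how the pre-treatment values enter the mixed model; constraining arms to equal baselines would narrow intervals at almost no cost

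*Combined protocol and SAP*

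**What the plan says.** Section 10.3 sets the outcome: "We will study changes over time in absolute levels of the primary and secondary end-points". The analysis is a repeated-measures mixed model. Its listed terms are treatment group, each treatment by time, the two treatments by each other, the three-way interaction with time, and "random-effects terms, connoting individual participants". No listed term is the endpoint's own baseline, and no statement sets arm means equal before treatment.

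The same section makes adjustment conditional on p<0.05 differences "in age, gender and baseline eGFR across randomized treatment groups, we will adjust for these covariates". It does not say whether one or all three must differ, or which are then entered.

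Sections 5.3, 5.4.1 and 5.5 collect the three primary endpoints, PTH and FGF23 at two pre-treatment visits, B1 and B2/F0. P1NP and CTX are measured at B1 and F5 only. No section says how these pre-treatment values enter the model. Section 5.4.1 also labels the second baseline as follow-up visit 0, and Section 10.2 says of the sample size: "we based our power calculations on t-tests that compare pre to post intervention changes across two groups". Both suggest that baseline visits are treated as part of the outcome series.

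**The concern.** In a randomized trial the arms have the same expected baseline. A model that estimates a separate baseline mean for each arm spends information on a difference known to be zero in expectation. It therefore behaves like a change-score analysis, which subtracts the whole baseline value even when the correlation with follow-up is well below 1. Using the baseline as a covariate, or constraining the baseline means, recovers that precision.

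Precision matters here because Section 1.1 says the results are meant to inform the design of CKD studies, and Section 10.2 says that data on nicotinamide in healthy volunteers and on the combination are lacking. Interval width is a main product of the trial. P1NP and CTX have one pre-treatment and one on-treatment value, so the gain that Section 10.2 expects from repeated measures cannot reach them.

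The covariate rule is a lesser matter. Baseline differences between randomized arms arise by chance, so a significance test across arms says nothing about whether a covariate predicts the endpoint. Because the trigger is ambiguous, two analysts could fit different models to the same data.

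**Working it through.** **Inputs from the plan.** 20 per arm, so 40 versus 40 for main effects; SD of change 300 mg/day for 24-hour urine phosphate; design difference 273 (printed in mg/dl in Section 10.2, read here as mg/day to match the SD).

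**Plan's own figure.** A two-sided two-sample t test with 38 df gives 80.1% power at 273 with SD 300. For plasma phosphate, 0.50 mg/dl with SD 0.55 gives 80.0%. Both reproduce.

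**Assumptions.** r is not in the documents, so r = 0.3/0.5/0.7/0.9 is used. Also assumed: equal variances, compound symmetry and complete data. The visit variance s² is set so that a single change has the plan's SD: 2s²(1−r) = 300².

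**Formulas.** With b baselines and m averaged follow-ups, per participant:
- change score: s²[(1+(m−1)r)/m + (1+(b−1)r)/b − 2r]
- baseline-adjusted: s²[(1+(m−1)r)/m − r²b/(1+(b−1)r)]

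For a linear-time slope with 7 visits, let c = r/(1+6r), S1 the sum of the times and S2 the sum of their squares. The ratio of the constrained to the free-baseline variance is 1 − S1²(1−7c)/[7(S2−cS1²)]. With time assumed 0 at both baselines and 2, 5, 8, 11, 14 days at F1 to F5, S1 = 40 and S2 = 410.

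**Variance ratios and narrowing of the 95% interval (1 − √ratio).**

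| Contrast | Ratio at r = 0.3/0.5/0.7/0.9 | Narrowing |
|---|---|---|
| Last visit, b=2, m=1 | 0.821/0.889/0.941/0.982 | 9/6/3/1% |
| Linear-time slope | 0.76/0.86/0.93/0.98 | 13/7/3/1% |
| Mean of five follow-ups, b=2, m=5 | 0.615/0.762/0.874/0.962 | 22/13/7/2% |
| P1NP and CTX, b=1, m=1; ratio (1+r)/2 | 0.65/0.75/0.85/0.95 | 19/13/8/3% |

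The (1+r)/2 ratio needs equal variances but not compound symmetry.

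**In endpoint units: 24-hour urine phosphate, five follow-ups averaged.** The change-score variance is 0.35 × 300² = 31,500 at every r. For a main effect the SE is √(31,500 × 2/40) = 39.7, and with t = 1.99 the half-width is 79 mg/day. Multiplying by √ratio gives 62/69/74/78. For dual treatment versus placebo (20 versus 20, 38 df) the half-width goes from 114 to 89/99/106/111.

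**If correlation decays with time instead** (r being the correlation between visits 3 days apart, visits equally spaced), the five-follow-up ratios are 0.369/0.461/0.605/0.836, which is 39/32/22/9% narrower.

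**Covariate rule.** Three independent tests at 0.05 flag at least one covariate by chance with probability 1 − 0.95³ = 14.3%. In a generalized least squares fit with free arm-by-visit means, 80 participants and seven complete visits, the dual-versus-placebo SE is √(31,500 × 2/20) = 56.12 mg/day. The estimate and SE are identical with and without three covariate main effects at every r, because a covariate that is constant within a person cancels from a within-person contrast. Under the equal-baseline model the covariates can move the estimate.

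**The case against.** **The list of terms may not be complete.** It names interactions with time but no time main effect, so it is plainly abbreviated, and a baseline term could have been intended. That is fair. It means the model is left open, which the same sentence of wording would settle.

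**Baseline is probably used already.** A reader might infer that the plan ignores baseline, or that its treatment effects are biased. The documents do not support that. The plan studies changes over time and sizes the trial on pre-to-post change. With baseline visits as outcomes, the contrast is a valid change score. Only the gap between change-score and baseline-adjusted precision is at stake.

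**The gain may be small.** r is unknown, and no passage says that follow-ups are averaged or how time is coded. The last-visit and linear-time figures are well below the averaged one, and at r = 0.9 every compound-symmetry figure is 3% or less. This stands, which is why all the contrasts are shown. The dual-versus-placebo comparison is also made only if the three-way interaction is significant, so the main-effect half-widths are the fairer illustration.

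**Power is already ample.** For dual versus placebo at 273 mg/day, the unadjusted contrast with two baselines has 89.9% power at the last visit (SD √67,500 = 259.8) and 99.7% with five averaged follow-ups. A reader might infer that the trial is underpowered without the change. It is not; the benefit is narrower intervals.

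**The covariate rule may change nothing.** On the likely reading with complete data, that is correct. A reader might take the 14.3% as inflated type I error, or expect power from age, sex and eGFR. Neither follows: it is only the chance that the rule is triggered, and the documents give no basis for the covariates' prognostic strength.

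**Conclusion.** The point stands as an inexpensive improvement in precision and pre-specification, not as an error of validity, type I error or sample size. Its main part is that the plan does not state how B1 and B2/F0 enter the model and lists neither a baseline term nor an equal-baseline constraint. Under compound symmetry and r from 0.3 to 0.9, the likely loss is 1 to 9% of interval width for a last-visit contrast, 1 to 13% for a linear slope, 2 to 22% for an average of five follow-ups, and 3 to 19% for P1NP and CTX. It is larger if correlation decays with time and small if r is high. The size rests on assumed r, equal variances and complete data; the direction does not depend on the value of r below 1.

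The covariate rule is secondary. It selects on chance imbalance and is ambiguous, but whether it can affect the treatment estimate depends on the unstated baseline handling.

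**What to change.** In Section 10.3, state that visit is a categorical factor and that arm means are constrained to be equal at baseline, with B1 and B2/F0 as baseline rows (B1 only for P1NP and CTX). Adjusting for the participant's mean baseline value of the endpoint is equivalent for this purpose; name one of the two as the analysis.

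Delete the p<0.05 condition. Either always include age, sex and baseline eGFR or omit them, and fix the choice before unblinding. If they are included, name the visit that supplies baseline eGFR, since creatinine is measured at screening, B1 and B2/F0. If baseline visits were instead kept as outcomes with free arm means, covariate-by-time terms would be needed for these covariates to affect the treatment contrast.

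The cost is wording only, as all the data are already collected. The endpoint baseline uses one degree of freedom: if it carried no information, the SE would rise by √(1+1/74), about 0.7%. Three covariates that were not prognostic would add √(1+3/72), about 2%. In simulation of 20,000 four-arm trials per r, with the cost of estimating the baseline slope included, the net narrowing was 21/12/6/1% for five averaged follow-ups and 19/13/7/2% for one baseline and one follow-up.

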11.0 STUDY MANAGEMENT**11.1 Conflict of Interest**

Any investigator who has a conflict of interest with this study (patent ownership, royalties, or financial gain greater than the minimum allowable by their institution, etc.) must have the conflict reviewed by the Feinberg School of Medicine. All investigators will follow the University conflict of interest policy.

11.2 Institutional Review Board (IRB) Approval and Consent

It is expected that the IRB will have the proper representation and function in accordance with federally mandated regulations. The IRB should approve the consent form and protocol.

In obtaining and documenting informed consent, the investigator should comply with the applicable regulatory requirement(s), and should adhere to Good Clinical Practice (GCP) and to ethical principles that have their origin in the Declaration of Helsinki.

Before recruitment and enrollment onto this study, the patient will be given a full explanation of the study and will be given the opportunity to review the consent form. Each consent form must include all the relevant elements currently required by the FDA Regulations and local or state regulations. Once this essential information has been provided to the patient and the investigator is assured that the patient understands the implications of participating in the study, the patient will be asked to give consent to participate in the study by signing an IRB-approved consent form.

Prior to a patient's participation in the trial, the written informed consent form should be signed and personally dated by the patient and by the person who conducted the informed consent discussion.

11.3 Registration Procedures

N/A

11.4 Subject Compensation

Subjects will receive compensation per study consent form. Study compensates \$50.00, in the form of a check, for each of the 8 study visits. Total compensation, excluding reimbursement for travel expenses, is \$400.00. Subjects will be required to submit proof of travel expenses (i.e., receipts) to study staff in order to be reimbursed for travel expenses. Travel expenses will be paid out in the form of a check as well.

11.5 Data Management and Monitoring/Auditing

The PI and Co-I will monitor data safety monitoring/management.

11.6 Adherence to the Protocol

Except for an emergency situation in which proper care for the protection, safety, and well-being of the study patient requires alternative treatment, the study shall be conducted exactly as described in the approved protocol.

11.6.1 Emergency Modifications

Investigators may implement a deviation from, or a change of, the protocol to eliminate an immediate hazard(s) to trial subjects without prior IRB approval.

For any such emergency modification implemented, a IRB modification form must be completed within five (5) business days of making the change.

11.6.2 Other Protocol Deviations/Violations

All other planned deviations from the protocol must have prior approval by the Principal Investigator and the IRB. According to the IRB, a protocol deviation is any unplanned variance from an IRB approved protocol that:

- Is generally noted or recognized after it occurs
- Has no substantive effect on the risks to research participants
- Has no substantive effect on the scientific integrity of the research plan or the value of the data collected
- Did not result from willful or knowing misconduct on the part of the investigator(s).

An unplanned protocol variance is considered a violation if the variance:

- Has harmed or increased the risk of harm to one or more research participants.
- Has damaged the scientific integrity of the data collected for the study.

- Results from willful or knowing misconduct on the part of the investigator(s).
- Demonstrates serious or continuing noncompliance with federal regulations, State laws, or University policies.

If a deviation or violation occurs without prior approval from the Principal Investigator, please follow the guidelines below:

Protocol Deviations: Deviations should be summarized and reported to the IRB at the time of continuing review.

Protocol Violations: Study personnel should report violations within one (1) week of the investigator becoming aware of the event using the same IRB online mechanism used to report Unanticipated Problems.

11.7 Amendments to the Protocol

Should amendments to the protocol be required, the amendments will be originated and documented by the Principal Investigator. It should also be noted that when an amendment to the protocol substantially alters the study design or the potential risk to the patient, a revised consent form might be required.

The written amendment, and if required the amended consent form, must be sent to the IRB for approval prior to implementation.

11.8 Record Retention

Study documentation includes all Case Report Forms, data correction forms or queries, source documents, Sponsor-Investigator correspondence, monitoring logs/letters, and regulatory documents (e.g., protocol and amendments, IRB correspondence and approval, signed patient consent forms).

Source documents include all recordings of observations or notations of clinical activities and all reports and records necessary for the evaluation and reconstruction of the clinical research study.

Government agency regulations and directives require that the study investigator must retain all study documentation pertaining to the conduct of a clinical trial. In the case of a study with a drug seeking regulatory approval and marketing, these documents shall be retained for at least two years after the last approval of marketing application in an International Conference on Harmonization (ICH) region. In all other cases, study documents should be kept on file until three years after the completion and final study report of this investigational study.

11.9 Obligations of Investigators

The Principal Investigator is responsible for the conduct of the clinical trial at the site in accordance with Title 21 of the Code of Federal Regulations and/or the Declaration of Helsinki. The Principal Investigator is responsible for personally overseeing the treatment of all study patients. The Principal Investigator must assure that all study site personnel, including sub-investigators and other study staff members, adhere to the study protocol and all FDA/GCP/NCI regulations and guidelines regarding clinical trials both during and after study completion.

The Principal Investigator at each institution or site will be responsible for assuring that all the required data will be collected and entered onto the Case Report Forms. Periodically, monitoring visits will be conducted and the Principal Investigator will provide access to his/her original records to permit verification of proper entry of data. At the completion of the study, all case report forms will be reviewed by the Principal Investigator and will require his/her final signature to verify the accuracy of the data.

13.0 APPENDICES

Appendix A.

Letter of IND exemption from the FDA
